4.4 Handling of missing and incomplete data

	Forms			
	Title	Statistical Analysis Plan Template		
	Code	Version	Effective Date	Page
	FRM_ST03_032	01	23 Apr 2015	15 of 20

The number of patients with missing data will be presented under the “Missing” category, if present. Missing values will be included in the denominator count when computing percentages.

When continuous data are being summarized, only the non-missing values will be evaluated for computing summary statistics.

A sensitivity analysis will also occur for the primary endpoint via a tipping point analysis. All missing data in the treatment group will be counted as failures while all missing data in the control group will be counted as successes. The p-values will be compared to the primary efficacy analysis to see if there is a difference in interpretation of results.

In general partial dates will be imputed as follows:

- if only the day is missing, the first day of the month will be assumed;
- if the day and the month are missing, January 1st will be assumed;
- if a date is completely missing or unknown the patient’s data will not be included for analysis

4.5 Software

All statistical analyses and data processing will be performed using Statistical Analysis Systems (SAS®) Software (release 9.2) on a Windows 7 or later operating system.

5. Evaluation of Demographic and Baseline Characteristics

5.1 Subject enrolment and disposition

The number of patients included in the randomized population, mITT, PP, safety, and AT populations will be also summarised.

5.2 Protocol violations

A protocol deviation is an instance of failure, intentionally or unintentionally, to follow the requirements of the protocol.

Deviations will be collected in the CRF and assessed according to the following categories:

- Intentional change to eliminate immediate hazard;
- Consent deviation (oral or written);
- Drug/device administration deviation (dosage, operation, schedule etc.);
- Enrollment deviation (inclusion/exclusion criteria, recruitment, etc.);
- Procedural deviation (research activities, research reporting etc);
- Subject non-compliance;
- Complaint from research subject;
- Audit finding that require corrective action;
- Failure to report AE and/or follow data/safety reporting procedures;

	Forms			
	Title	Statistical Analysis Plan Template		
	Code	Version	Effective Date	Page
	FRM_ST03_032	01	23 Apr 2015	16 of 20

- Breach of confidentiality
- Other.

During data review process before the database lock, protocol deviations will be classified as major protocol deviation and minor protocol deviation.

Major and minor protocol deviations will be summarized for each treatment arm and overall. Major deviations from the protocol will lead to the exclusion of the patient from the PP population.

5.3 Study discontinuations

Patients discontinued from the study prematurely will be presented for the randomized patients, with a breakdown of the reasons for discontinuation as reported in the CRF.

5.4 Demographics and baseline characteristics

The demographic and baseline characteristics will be summarised by treatment arm and overall by means of descriptive statistics.

The following demographic characteristics will be provided for the randomized patients:

- Age, gender, race, surgical risk factors, pre-operative diagnosis.
- Vital signs (heart rate and blood pressure), height and weight.
- Serum tests (total bilirubin, creatinine, serum sodium and INR) for MELD Score.
- Pregnancy test (urine test or institution standard of care) for females of childbearing potential.

5.5 Medical History

Medical history and concomitant diseases will be coded using Medical Dictionary for regulatory activities (MedDRA) dictionary (version 18.0) and frequency distributions and percentages will be summarised by treatment and overall for the randomised patients by SOC and PT.

5.6 Prior and concomitant medications

Any concomitant medications the subject is receiving at the start of the study (Day 0) or given for any reason during the study will be summarised by treatment and overall for the safety population through frequency distributions and percentages by Anatomical Main Group (1st level of the Anatomical Therapeutic Chemical (ATC) classification), Chemical Subgroup (2nd level of ATC classification) and Preferred Name.

6. Evaluation of Efficacy

	Forms			
	Title	Statistical Analysis Plan Template		
	Code	Version	Effective Date	Page
	FRM_ST03_032	01	23 Apr 2015	17 of 20

6.1 Analysis of primary endpoint

The primary objective is to demonstrate an improvement in post-operative anastomotic leak rate in low anterior resection procedures where colon and rectal tissue perfusion is evaluated using PINPOINT or SPY Elite near infrared fluorescence imaging as an adjunct to standard surgical practice compared to surgical procedures performed according to standard surgical practice alone.

$$H_0: p_t = p_c$$

$$H_1: p_t < p_c$$

Where p_t and p_c represent the expected population incidences of post-operative anastomotic leaks in the treatment (PERFUSION) and control groups, respectively. Within their respective treatment groups, p_t and p_c will be estimated as the number of subjects who experience a post-operative anastomotic leak divided by the number of subjects who either are included in the numerator or are known to be free of such leaks as of the 8 weeks visit. Subjects without a known anastomotic leak but with less than 6 weeks of follow-up (i.e., insufficient follow-up to declare them "leak-free") will not be included in these estimates.

Analysis of these hypotheses will be conducted using a z-test (i.e., normal approximation to the binomial distribution, using a pooled variance estimate and without continuity correction), using a (one-sided) significance level of 0.025.

A secondary analysis of the primary endpoint will be carried out on the As-treated population as well as on the PP population.

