### 10.3 Statistical Analysis

Analysis of these hypotheses will be conducted using a z-test (i.e., normal approximation to the binomial distribution, using a pooled variance estimate and without continuity correction), using a (one-sided) significance level of 0.025.

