3.1 General design and plan

This is a randomized, controlled, parallel, multicenter study to determine the reduction in post-operative anastomotic leak rate in low anterior resection (LAR) procedures where colon and rectal tissue perfusion is evaluated using PINPOINT or SPY Elite as an adjunct to standard surgical practice compared to surgical procedures performed according to standard surgical practice alone. Subjects will be enrolled at up to 40 centers in North America through March 31, 2017. The study sample size will depend on the number of subjects enrolled.

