3.4 Randomization and blinding

Patients will be prospectively randomized into the PILLAR III Clinical Trial. Randomization will occur at the time of surgery, just after induction of anesthesia. Prior to surgery the patient will have provided written informed consent, completed all baseline procedures and met the requirements of the study inclusion and exclusion criteria. Randomization should be performed as closely as possible to the point of resection to minimize the incidence of dropout.

Patients will be randomly assigned on a one to one (1:1) basis to either the PERFUSION group (PFN) or the STANDARD group (STD). Randomization will be stratified by study site and within site by the patients history of prior neoadjuvant therapy (chemotherapy and/or radiation vs. non-neoadjuvant therapy) to ensure a more even distribution of baseline neoadjuvant therapy between treatment groups. Permuted block randomization will be performed within strata. To minimize the opportunity for the sequence to be predicted, the block size will be variable and randomly chosen from small multiples of 2 (i.e. 2, 4 or 6). The randomization schedules for all strata will be generated in advance by the contracted study statistician or designee using a computerized random number generator. Investigational sites and the Study Sponsor will not have access to the randomization schedules.

Randomization will be accomplished using a sequential numbered sealed envelope system. Due to stratification for prior neoadjuvant therapy, a box of envelopes will be supplied for each strata (one for subjects who have received prior neoadjuvant therapy and another for subjects who have not received prior neoadjuvant therapy). Envelope seals are broken and treatment assignment is made only after verification of proper informed consent execution and study eligibility. In order to prevent any attempts to subvert the randomization process, the subject's initials, date of birth, and date of randomization will be written on the randomization card. The randomization card will be signed by the study coordinator performing the randomization procedure and a second researcher who will witness the randomization procedure.

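### The primary leak test ignores the factors used to stratify randomisation; it is valid, at most mildly conservative, and cheaply improved by stratifying on neoadjuvant therapy

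*SAP*

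**What the plan says.** Both documents stratify the allocation in the same way. SAP 3.4 (repeated in Protocol 5.1) says: "Randomization will be stratified by study site and within site by the patients history of prior neoadjuvant therapy". Allocation is 1:1 by permuted blocks, and "the block size will be variable and randomly chosen from small multiples of 2 (i.e. 2, 4 or 6". SAP 3.1 allows up to 40 centres, so there may be up to 80 site-by-neoadjuvant strata.

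The primary test uses neither factor. Protocol 10.3 begins "Analysis of these hypotheses will be conducted using a z-test", and SAP 6.1 specifies the same test: "Analysis of these hypotheses will be conducted using a z-test (i.e., normal approximation to the binomial distribution, using a pooled variance estimate", with no continuity correction and "using a (one-sided) significance level of 0.025".

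Centre appears in one model only, the poolability logistic regression of SAP 4.3, after which the data are analysed as if from one site. Neoadjuvant therapy appears in no analysis model. SAP 4.1 promises 95% intervals for the primary endpoint, which SAP 3.5.1 defines as the incidence in each arm. SAP 6.1 names no interval for the difference in leak rates, although SAP 6.2 names one for the secondary abscess endpoint.

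**The concern.** Stratified blocks keep the arms alike on site and neoadjuvant therapy, so differences in leak risk between strata contribute little to the sampling error of the treatment difference. A pooled unstratified variance still counts them. If the strata are prognostic, the computed standard error is too large, the test runs slightly under its nominal level, and precision that the design has already paid for is not used.

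There are qualitative grounds for expecting some prognostic effect. Protocol 1.1 lists radiation exposure among factors for anastomotic complications and cites leak rates from 3 to 20%. The SAP 4.3 check does not settle the matter: it tests the treatment-by-centre interaction, and a non-significant interaction says nothing about whether baseline leak risk is equal across sites.

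At stake is a small amount of power, in a trial whose SAP (3.3) replaces the planned 800 subjects with whoever has enrolled by 31 March 2017, together with a properly specified effect estimate.

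**Working it through.** **Step 1. Reproduce the protocol's power.** Inputs from Protocol 10.4 and the paragraph headed 10.5: rates 12.5% and 6.25%, looks at 450 and 800, Pocock-type spending, one-sided 0.025.
- Alpha spent at t = 450/800 = 0.5625: 0.025 × ln(1 + (e − 1) × 0.5625) = 0.0169, as stated.
- Boundaries with correlation √0.5625: z = 2.122 and 2.220.
- Pooled rate 0.09375, variance 0.09375 × 0.90625 = 0.08496. Drift: 0.0625/√(2 × 0.08496/225) = 2.274 and 0.0625/√(2 × 0.08496/400) = 3.032.
- Power = 81.6%, as stated. The published power belongs to the unstratified test.

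**Step 2. Neoadjuvant therapy alone.** Assumptions, not in the documents: 60% neoadjuvant, control rate 12.5% overall, leak rate halved in every stratum. The pooled rate in a stratum is then 0.75 times its control rate.
- Between-stratum variance = 0.6 × 0.4 × (0.75 × gap in control rates)².
- Odds ratio 2 (control 15.32% and 8.30%): 0.24 × (0.75 × 0.0702)² = 0.000665. Within/total = 1 − 0.000665/0.08496 = 0.992. Standard error too large by 1/√0.992 − 1 ≈ 0.39%.
- Odds ratios 1.5 and 3 give 0.14% and 0.88%.
- Fixed-design power at N = 800 moves from 86.0% to 86.1%, 86.2% and 86.6% for odds ratios 1.5, 2 and 3: a gain of 0.1 to 0.6 points. This slightly flatters stratification, because it holds the unstratified power at its no-effect value.

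**Step 3. Both factors, large-stratum limit, two-look design.** The SD is the assumed between-site spread of log-odds. Power uses a pooled null and unpooled alternative variance, which gives 81.7% with no stratum effect.

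| Odds ratio, site SD | SE too large by | True one-sided level | Power, unstratified | Power, stratified |
|---|---|---|---|---|
| 1, 0 | 0% | 0.0250 | 81.7% | 81.7% |
| 1.5, 0.3 | 0.5% | 0.0244 | 81.8% | 82.1% |
| 2, 0.5 | 1.4% | 0.0234 | 82.0% | 82.9% |
| 3, 0.8 | 3.6% | 0.0212 | 82.5% | 84.5% |

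**Step 4. Real, sparse strata.** Simulated single-look trials with stratified permuted blocks, 12.5% against 6.25%. Power in per cent; N = 350 is an assumed smaller enrolment. CMH is the Cochran-Mantel-Haenszel test.

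| N, sites, odds ratio, SD | z-test | CMH, all site × neoadjuvant cells | CMH, neoadjuvant only |
|---|---|---|---|
| 800, 40, 2, 0.5 | 85.68 | 85.73 | 85.73 |
| 800, 40, 3, 0.8 | 87.53 | 88.18 | 87.75 |
| 350, 25, 2, 0.5 | 51.92 | 51.56 | 52.29 |
| 350, 25, 3, 0.8 | 53.39 | 54.20 | 53.94 |
| 350, 40, 1.5, 0.3 | 52.71 | 49.65 | 52.82 |

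Simulation error is about 0.5 points on each power, but the tests are compared on the same trials. Neoadjuvant-only stratification gained 0.05 to 0.55 points; the full cross-classification ranged from −3.1 to +0.8.

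Further runs with 40 sites gave these changes against the z-test:
- all cells: −4.4 to +1.0 points (worst: 52.6% to 48.2%, N = 350, non-prognostic strata);
- neoadjuvant only: about 0 to +0.9;
- sites under 20 subjects pooled: −0.4 to +1.2.

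At N = 450, the protocol's interim size, the all-cells test took power from 63.7% to 62.1% (odds ratio 2, SD 0.5) and from 61.4% to 58.9% (no stratum effect). With small sites pooled, null rejection was 0.019 to 0.027, compatible with 0.025 given simulation error of about 0.0025.

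**The case against.** The strongest reply is that nothing here is an error. The z-test is valid, any departure is conservative, and its power was computed for the test specified. Analysing sites together is a stated choice with a rationale in Protocol 10.9. Blocks of at most 6 already cap imbalance at 3 subjects per stratum, in random directions. All of this stands.

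A reader might infer three stronger things that the documents do not support. The first is that the standard error is certainly too large and power certainly lost. That holds only if leak risk differs across strata; the documents give no rates by site or neoadjuvant status, and with non-prognostic strata the loss is zero. The second is that the mismatch inflates false positives or undermines the 81.6%. Step 1 reproduces that figure, and the level in Step 3 never exceeds 0.025. The third is that stratifying on every randomisation cell is free. Step 4 shows that it can cost several points when strata are sparse, because cells containing one arm only contribute nothing.

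The missing interval for the primary difference is a separate reporting gap that could be closed without stratifying. It is convenient to close both together.

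**Conclusion.** The mismatch between stratified randomisation and an unstratified primary test is real and appears in both documents. Its consequence is small: a valid test that is mildly conservative if the strata are prognostic. The power forgone is about 0 to 1 points in realistic cases and about 2 at most, the latter in a large-stratum limit with an odds ratio of 3 and a site SD of 0.8. These sizes rest on an assumed 60% neoadjuvant share, assumed stratum effects and the protocol's 12.5% and 6.25%; the SAP fixes no sample size. This is a worthwhile, nearly free improvement in efficiency and reporting, and validity is not in question.

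**What to change.** In Protocol 10.3 and SAP 6.1, make the primary test a Cochran-Mantel-Haenszel test, one-sided at 0.025, stratified by prior neoadjuvant therapy. Add site only with a small-site rule written down before unblinding, for example all sites with fewer than 20 analysed subjects pooled into one stratum. Do not stratify over all site-by-neoadjuvant cells. Report the Mantel-Haenszel difference in leak rates with its 95% confidence interval, and keep the unstratified z-test as a supportive analysis.

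The cost is protocol and SAP wording and a few lines of code, with no new data. If the strata turn out not to be prognostic, the change in power is negligible.

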6.2 Analysis of secondary efficacy endpoints

The secondary efficacy endpoints are:

- To evaluate the ability of the PINPOINT system or SPY Elite system to provide sufficient visualization for assessment of blood flow and related tissue perfusion during the procedure.
 - This will be analyzed by comparing the PERFUSION-group proportion of subjects for whom there was sufficient visualization for assessment of blood flow and related tissue perfusion to a predetermined proportion, eg. 0.9.
- To evaluate the effectiveness of assessing perfusion of colon and rectal tissue using PINPOINT or SPY Elite in reducing the rate of post-operative abscess requiring surgical management.
 - This will be analyzed by comparing the treatment group and control group incidence of post-operative operative abscess requiring surgical management

These objectives are intended to support product labeling and will be tested in sequential fashion, i.e., if and only if the primary objective passes, testing will proceed to the first secondary objective below (proportion of PERFUSION arm subjects in whom the PINPOINT or SPY Elite system provided sufficient visualization for assessment of blood flow and related tissue perfusion during

	Forms			
	Title	Statistical Analysis Plan Template		
	Code	Version	Effective Date	Page
	FRM_ST03_032	01	23 Apr 2015	18 of 20

the procedure). If and only if that objective passes, testing will proceed to the second secondary objective (incidence of abscess requiring surgical management). The standard for “passing” the secondary objectives will be a p-value less than 0.025 one sided.

To evaluate the ability of the PINPOINT or SPY Elite system to provide sufficient visualization for assessment of blood flow and related tissue perfusion during the procedure:

The statistical threshold for study success will be sufficient visualization for assessment of blood flow and related tissue perfusion in greater than 90% of subjects. Letting p_t represent the PERFUSION-group proportion of subjects for whom there was sufficient visualization for assessment of blood flow and related tissue perfusion, the following hypotheses will be tested:

$$H_0: p_t \leq 0.9$$

$$H_1: p_t > 0.9$$

The statistical test will be a one-sided exact binomial test of proportions. Descriptive statistics and 95% confidence intervals will be calculated for p_t .

To evaluate the effectiveness of assessing perfusion of colon and rectal tissue using PINPOINT or SPY Elite in reducing the incidence of post-operative abscess requiring surgical management:

Letting p_t and p_c respectively represent the treatment-group and control-group incidence of post-operative abscess requiring surgical management, the following hypotheses will be tested:

$$H_0: p_t = p_c$$

$$H_1: p_t < p_c$$

The statistical test will be a z-test using pooled variance estimate and no continuity correction. In the case of small counts, an exact procedure will be used. Descriptive statistics and 95% confidence intervals will be calculated for p_t , p_c , and $(p_t - p_c)$.

Then secondary efficacy endpoints will be analyzed on the mITT population.

7. Evaluation of Safety

The number of AEs, ADEs, SAEs, UADEs, and the number and the percentage of patients experiencing AEs, SAEs, ADEs, UADEs will be presented for the safety set.

AEs will be coded using the MedDRA dictionary (version 18.0). The SOCs and PTs will be used for tabulation.

The number of AEs and the number and the percentage of patients with at least one AE will be presented by SOC and PT for AEs, SAEs.

	Forms			
	Title	Statistical Analysis Plan Template		
	Code	Version	Effective Date	Page
	FRM_ST03_032	01	23 Apr 2015	19 of 20

All adverse events and post-operative complications occurring during the study period will be graded according to the Clavien-Dindo classification system.

The number and the percentage of patients with at least one AE and ADE will be presented by SOC, PT and Clavien-Dindo classification system.

7.1 Adverse events (AE)

Any untoward medical occurrence, unintended disease or injury or any untoward clinical signs (including an abnormal laboratory findings) in subjects whether or not related to the investigational medical device.

7.2 Adverse Device Effect (ADE)

Any adverse event related to the use of PINPOINT or SPY Elite (includes imaging agent and all hardware components).

7.3 Serious Adverse Event (SAE)

Any adverse event that:

- a. Led to a death.
- b. Led to a serious deterioration in health that either:
 - i. Resulted in a life-threatening illness or injury,
 - ii. Resulted in a permanent impairment of a body structure or a body function,
 - iii. Required in-patient hospitalization or prolongation of existing hospitalization,
 - iv. Resulted in medical or surgical intervention to prevent life threatening illness or injury or permanent impairment to a body structure or a body function.
- c. Led to fetal distress, fetal death or a congenital abnormality or birth defect.

7.4 Unanticipated Adverse Device Effect (UADE)

Any ADE that meets the following:

- By its nature, incidence, severity or outcome has not been identified in the current version of the PINPOINT (or SPY Elite if applicable) risk analysis report.
- On health or safety, any life-threatening problem or death caused by, or associated with a device, if that effect, problem, or death was not previously identified in nature, severity, or

	Forms			
	Title	Statistical Analysis Plan Template		
	Code	Version	Effective Date	Page
	FRM_ST03_032	01	23 Apr 2015	20 of 20

degree of incidence in the application; or any other unanticipated serious problem associated with a device that relates to the rights, safety, or welfare of subjects.
